6.4 Echocardiographic imaging

Echocardiographic data will be collected from the TEE and TTE images for the corelab interpretation of the degree of TR reduction and adverse events, if any. A physician or sonographer familiar with valvular heart disease and experienced in performing echocardiograms should perform each assessment. 

	TRI-REPAIR – Tricuspid Regurgitation RePAIR with Cardioband Transcatheter System (TR1-1). Study protocol	
---	---	---

6.5 Subject withdrawal

6.5.1 Withdrawal

Subjects may withdraw from the study at any time for any reason, according to the terms of the Informed Consent document, which includes continuation of clinical study follow-up whenever possible, and ongoing medical care as appropriate. Subjects may also be withdrawn from the study at any time at the discretion of the investigator.

It should be understood that an excessive rate of withdrawals could render the study difficult to interpret. Hence, unnecessary withdrawal of subjects should be avoided. Should a subject withdraw or is withdrawn, every effort must be made to complete and report the observations as thoroughly as possible. If possible, in case of withdrawal, permission for yearly study telephone follow up to assess long-term outcomes and safety will be obtained from the subject.

6.5.2 Procedures for handling withdrawal

Subjects who withdraw or are withdrawn from the study should:

- Have the reason(s) for their withdrawal recorded (if possible).
- May be seen by an investigator and all final assessments should be performed and recorded.
- Be asked about the presence of any AEs. If an ongoing AE is present, the patient should be followed up until satisfactory clinical resolution of the event is achieved.

If a subject is withdrawn, Valtech monitor should be informed as soon as possible by the site. One additional subject will be enrolled for each subject withdrawn (or died) for any reason before the primary endpoint period completed.

For each patient with missing significant data for the primary endpoint, such as data regarding performance (access, deployment and positioning) of the Cardioband device, and/ or missing an Echocardiography, an additional patient will be recruited.

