5.3 Study Endpoints

5.3.1 Primary endpoints

Safety:

Overall rate of Major Serious Adverse Events (MSAEs)* and serious adverse device effects (SADE) until hospital discharge and at post-operative 30 days.

* Death, myocardial infarction, cardiac tamponade, device related cardiac surgery, stroke.

Technical Success:

Successful access, deployment and positioning of the Cardioband device and septolateral reduction at intra-procedure and discharge

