5.5 Statistical Considerations

5.5.1 Sample size

A sample size of up to 60 patients, enrolled in this proposed multi-center study, is considered adequate to further confirm the safety and performance of the Cardioband System in TR patients. Considerable clinical data on the safety of clinically equivalent devices exists, this will enable a comparison of the clinical data obtained in this study of the safety and performance of the Cardioband System, with literature data from prior studies.

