5.5.2 Sample size Justification

Reference values for calculations are based on a literature review of predicate devices [REDACTED] and clinical experience in previous studies of Valtech adjustable mitral annuloplasty devices [REDACTED].

Therefore, this sample size allows accurate estimates of risk associated with the device even for rare events.

The sample size for the study was selected through the width of the two-sided exact 95% confidence interval of the potential adverse event rates. [REDACTED]

[REDACTED]	■	[REDACTED]	[REDACTED]	[REDACTED]
[REDACTED]	■	[REDACTED]	[REDACTED]	[REDACTED]
[REDACTED]	■	[REDACTED]	[REDACTED]	[REDACTED]
[REDACTED]	■	[REDACTED]	[REDACTED]	[REDACTED]

Rates for anticipated complications (adverse events) will be compared with historical data on morbidity and mortality in similar populations and for analogous devices.

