6.5.3 Lost to follow up

If a subject does not appear for a follow-up visit and cannot be contacted for collecting follow-up information the primary physician will be contacted and will be asked about the subject's health condition. At least 3 attempts should be made to contact the subject through all available routes attempt to contact the patient should be recorded. If there is no contact with the patients and/or primary physician - he/she will be considered 'lost to follow up'. One additional subject may be enrolled for each lost to follow up before the primary endpoint period completed.

	TRI-REPAIR – Tricuspid Regurgitation RePAIR with CaRdioband Transcatheter System (TR1-1). Study protocol	
---	---	---

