3.4 Missing data handling

All statistical analysis on primary and secondary endpoints will be performed using only available data. No missing value imputation will be performed.

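### Protocol 6.5.2 replaces subjects who die or withdraw before the primary endpoint period ends; deaths stay in the safety analysis, but subjects with unknown 30-day status drop out of the rate and no planned analysis bounds it

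*Protocol*

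**What the plan says.** **Replacement.** Protocol 6.5.2, on handling withdrawal, states: "One additional subject will be enrolled for each subject withdrawn (or died) for any reason before the primary endpoint period completed". Its next paragraph adds a further patient in another case: "For each patient with missing significant data for the primary endpoint". For loss to follow-up, Protocol 6.5.3 is optional rather than mandatory: "One additional subject may be enrolled for each lost to follow up before the primary endpoint period completed".

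**Endpoint.** Protocol 5.3.1 defines the primary safety endpoint as "Overall rate of Major Serious Adverse Events (MSAEs)* and serious adverse device effects (SADE) until hospital discharge and at post-operative 30 days". The MSAEs are "Death, myocardial infarction, cardiac tamponade, device related cardiac surgery, stroke". SAP 2.1 and 3.2 carry the same five components to discharge and 30 days.

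**Analysis sets.** Protocol 5.5.3 runs the safety analyses on all subjects. SAP 2.3 puts every consented, eligible subject with an attempted procedure into the ITT cohort, and analyses primary safety in both the ITT and the as-treated cohorts.

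**Missing data.** SAP 3.4: "All statistical analysis on primary and secondary endpoints will be performed using only available data". It rules out imputation.

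**Sample size.** Protocol 5.5.1: "A sample size of up to 60 patients, enrolled in this proposed multi-center study". Neither document says whether this number includes replacements, and the SAP does not mention replacement at all.

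**The concern.** Replacement makes sense when a subject leaves before the outcome is known. A subject who dies before day 30 has reached the primary safety endpoint, so nothing is missing for safety. Enrolling another subject because of the death makes the number enrolled depend on the outcome being estimated.

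Withdrawn and lost subjects are a different matter. Their 30-day status may really be unknown, and the reason they left may be related to how they were doing. If they drop out of the denominator while new subjects come in, the study reports about its planned number with known status, and the rate itself carries no sign of what is unknown.

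The level of the rate matters because there is no control arm. Protocol 5.5.2 compares complication rates with historical data, so a rate that is too low feeds straight into that comparison.

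**Working it through.** **Plan's own figure.** Protocol 5.5.2: "The sample size for the study was selected through the width of the two-sided exact 95% confidence interval of the potential adverse event rates". The reference rates and target widths are blacked out, so 60 can be neither reproduced nor refuted. For orientation, the two-sided exact (Clopper-Pearson) 95% interval at n = 60 is 1.0-13.9% for 3 events and 3.8-20.5% for 6 events.

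**Assumptions.** The readable text gives no expected 30-day rate of death, MSAE or withdrawal, so all counts below are assumed and shown as a range. The primary endpoint period is taken as 30 days. Replacements are taken to come on top of 60.

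**Step 1: deaths.** With d deaths by day 30, all kept in the ITT cohort, the rate is d/60 without replacement and d/(60 + d) with it.

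| d | d/60 (exact 95% CI) | d/(60 + d) (exact 95% CI) |
|---|---|---|
| 1 | 1.7% (0.0-8.9) | 1/61 = 1.6% (0.0-8.8) |
| 3 | 5.0% (1.0-13.9) | 3/63 = 4.8% (1.0-13.3) |
| 6 | 10.0% (3.8-20.5) | 6/66 = 9.1% (3.4-18.7) |

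On average the dilution is smaller still. If enrolment runs until 60 subjects survive the period, d follows a negative binomial distribution, P(d) = C(59 + d, d) p^d (1 - p)^60. The expected value of d/(60 + d) is then 1.97%, 4.92% and 9.85% for assumed true rates p of 2%, 5% and 10%.

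The chance that at least one death triggers a replacement is 1 - (1 - p)^60, which is 70%, 95% and 99.8% at the same rates. The rule would probably be used, but its effect on the death rate is slight.

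**Step 2: unknown 30-day status.** Let 60 subjects have known status, 3 of them with an MSAE, and let u more attempted subjects have withdrawn or been lost with no event recorded and status unknown. Under the available-data rule the rate is 3/60 whatever u is. With unknowns counted as events it is (3 + u)/(60 + u).

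| u | As observed | Unknowns as events (exact 95% CI) |
|---|---|---|
| 1 | 3/60 = 5.0% (1.0-13.9) | 4/61 = 6.6% (1.8-15.9) |
| 2 | 3/60 = 5.0% (1.0-13.9) | 5/62 = 8.1% (2.7-17.8) |
| 3 | 3/60 = 5.0% (1.0-13.9) | 6/63 = 9.5% (3.6-19.6) |
| 6 | 3/60 = 5.0% (1.0-13.9) | 9/66 = 13.6% (6.4-24.3) |

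At u = 3 the point estimate moves by 9.5 - 5.0 = 4.5 percentage points and the upper limit by 19.6 - 13.9 = 5.7.

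If 60 is instead a ceiling on all attempts, the same assumed counts (3 events, 3 unknown) give 3/57 = 5.3% as observed and 6/60 = 10.0% with unknowns as events. The gap does not depend on how the ceiling is read.

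**The case against.** **The analysis sets already protect deaths.** This stands. The rule adds a subject and nowhere deletes one. A reader might infer that replaced deaths vanish, so that fatal events read 0/60 (0-6.0%). That would need a cohort of subjects who completed the primary period, and neither document defines one. SAP 2.1, 3.2 and 4.2.1 list death as an MSAE component, and SAP 2.3 keeps every attempted subject.

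**The losses are visible.** This also stands. Protocol 5.5.3 requires numbers per visit, reasons for discontinuation and a list of discontinued subjects. SAP 4.1.2 tabulates deaths, withdrawals and losses at 30 days. These tables show how many are missing, but no planned analysis carries that number into the MSAE rate.

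**A death can leave something to replace.** Technical success includes septolateral reduction at discharge, and a death before discharge can leave that unmeasured. This is true, but the sentence in 6.5.2 on missing primary endpoint data already covers it, so '(or died)' is not needed for that purpose.

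**Few statuses will be unknown.** Protocol 6.5.1 to 6.5.3 ask for final assessments, adverse event enquiry, at least three contact attempts and contact with the primary physician. SAP 3.4 does not remove an MSAE recorded before withdrawal. Both facts reduce u; neither makes it zero.

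**There are no pre-specified hypotheses (SAP 3.1).** This is correct, so no test is invalidated. The estimate and its comparison with historical rates are what is affected.

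**Conclusion.** The point holds in a limited form. For deaths, the rule creates an outcome-dependent sample size and a slight dilution (4.8% against 5.0% with 3 deaths). It does not remove deaths from the safety analysis, and the documents do not support reading it that way.

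The part with real effect is the unknown 30-day status of withdrawn or lost subjects. With 3 unknowns and 3 observed events, the rate could lie anywhere from about 5% to 9.5%, and the plan would report only the lower end. The upper figure is a bound, not an estimate. It rests on assumed counts, and its width grows with the number unknown.

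Two matters stay open in the text: whether 60 includes replacements, and an explicit statement that replaced subjects remain in the ITT cohort. Label: cheap improvement.

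**What to change.** 1. Protocol 6.5.2: delete '(or died)'.
2. SAP 2.3: state that every subject with an attempted procedure stays in the ITT numerator and denominator whether or not a further subject is enrolled, and say whether 60 includes replacements.
3. SAP 3.2 and 3.4: add one sensitivity row giving the 30-day MSAE rate in all attempted subjects, with unknown status counted as an event and an exact 95% interval, beside the available-data rate.

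Cost: a short protocol edit, a short SAP addition and one table row. The downside is that the sensitivity rate may look less favourable than the available-data rate.

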6.5.3 Lost to follow up

If a subject does not appear for a follow-up visit and cannot be contacted for collecting follow-up information the primary physician will be contacted and will be asked about the subject's health condition. At least 3 attempts should be made to contact the subject through all available routes attempt to contact the patient should be recorded. If there is no contact with the patients and/or primary physician - he/she will be considered 'lost to follow up'. One additional subject may be enrolled for each lost to follow up before the primary endpoint period completed.

	TRI-REPAIR – Tricuspid Regurgitation RePAIR with CaRdioband Transcatheter System (TR1-1). Study protocol	
---	---	---

6.6 Screening failure

A screening failure will be defined as patient who fulfilled the theoretical eligibility criteria, and was intended to treat, however Cardioband was not be implanted due to new information detected at the time of procedure, preventing the implantation. A screening failure will be followed until discharge from hospital.

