Procedure	The system will be delivered percutaneously via the femoral vein. The procedure will be guided by fluoroscopy and trans-esophageal / intracardiac echocardiography
Follow-Up Schedule	1 month: 30 ± 14 days 6 Months: 180 ± 30 days 12 Months: 365 ± 30 days 24 Months: 730 ± 30 days Subjects in whom no devices are implanted will be followed for 6 months.
Follow Up Evaluations	Key Pre-Implantation Procedures: 
 1. History and Physical 2. TTE , TEE and/or CT angiography and/or MRI 3. 6 minute walk test 4. KCCQ Key Post-Procedure Procedures: 
 1. Serial AE assessment, history, and physical at 30 days, 6 months, 12 months, 24 months) 2. Serial TTEs (30 days, 6 months, 12 months, 24 months) 3. Cardiac MRI at 6 months (optional) 4. 6 minute walk tests (30 days, 6 months, 12 months, 24 months) 5. KCCQ
Clinical Event Committee	An independent Clinical Event Committee will adjudicate all Serious Adverse events.
First subject in	
Last subject in	

	TRI-REPAIR – Tricuspid Regurgitation RePAIR with Cardioband Transcatheter System (TR1-1). Study protocol	[REDACTED] [REDACTED] [REDACTED]
---	---	--

Last follow-up	[REDACTED] [REDACTED] [REDACTED]
----------------	----------------------------------

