6.2 Exclusion criteria

Patients who fulfill any of the following criteria may not participate in this study.

1. Aortic, mitral and/or pulmonic valve stenosis and/or regurgitation \geq moderate
2. Severe uncontrolled hypertension (SBP ≥ 180 mmHg and/or DBP ≥ 110 mm Hg)
3. Previous tricuspid valve repair or replacement
4. Presence of trans-tricuspid pacemaker or defibrillator leads which cause impingement of the tricuspid valve leaflet as evaluated by echocardiography.

5. Active endocarditis
6. MI or known unstable angina within the 30 days prior to the index procedure
7. Any PCI or transcatheter valvular intervention within 30 days prior to the index procedure
8. Hemodynamic instability or on IV inotropes
9. Cerebrovascular Accident (CVA) within the past 6 months
10. Subject is on chronic dialysis
11. Anemia (Hb < 9 g/L) not corrected by transfusion
12. Bleeding disorders or hypercoaguable state
13. Active peptic ulcer or active gastrointestinal (GI) bleeding
14. Contraindication to anticoagulants
15. Known allergy to stainless steel, nickel, and/or polyester
16. Pregnant or lactating; or female of childbearing potential with a positive pregnancy test 24 hours before any study-related radiation exposure
17. In the judgment of the Investigator, co-morbid condition(s) that could limit the subject's ability to participate in the study, including compliance with follow-up requirements, or that could impact the scientific integrity of the study
18. Life expectancy of less than 12 months
19. Impaired judgment and/or is undergoing emergency treatment
20. Currently participating in another investigational drug or device study that has not completed the primary endpoint or that clinically interferes with the endpoints of this study
21. Intra-cardiac masses, thrombi or vegetations
22. Patients with cardiac cachexia
23. Subjects in whom transesophageal echocardiography is contraindicated
24. Known hypersensitivity or contraindication to procedural medications which cannot be adequately managed medically
25. Untreated clinically significant CAD requiring revascularization
26. Echocardiographic evidence of severe right ventricular dysfunction
27. Any coronary or endovascular surgery, within 3 months prior to procedure

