2.3 Analysis populations

Two analysis cohorts will be defined as below:

- Intent-to-treat (ITT) cohort includes all subjects who signed informed consent, met eligibility criteria, and for whom the study procedure has been attempted.
- As-treated cohort is a subject of the ITT cohort and includes all subjects for whom the study device is implanted and remains in the position at the time of the subject's exit from the procedure room.

The primary safety analysis will be performed on both cohorts with due consideration given to the required follow-up intervals for each cohort. All other analyses will be performed on the as-treated cohort.

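### Protocol 6.6 and the synopsis set different follow-up for the same non-implanted patient, so 30-day safety status in the ITT cohort can go unobserved

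*Protocol*

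**What the plan says.** Protocol 6.6 applies the term screening failure to someone intended for treatment who met the eligibility criteria in theory and did not receive the device. The reason for stopping is part of the definition: "however Cardioband was not be implanted due to new information detected at the time of procedure, preventing the implantation". The follow-up rule for this group is: "A screening failure will be followed until discharge from hospital".

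The Follow-Up Schedule in the protocol synopsis has a general rule with no exception: "Subjects in whom no devices are implanted will be followed for 6 months".

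The primary safety endpoint is assessed at hospital discharge and at 30 days (Protocol 5.3.1, SAP 2.1). SAP 2.3 analyses it on two cohorts. The ITT cohort is "all subjects who signed informed consent, met eligibility criteria, and for whom the study procedure has been attempted"; the as-treated cohort requires a device in place when the subject leaves the procedure room. SAP 2.3 says the safety analysis is done on both "with due consideration given to the required follow-up intervals for each cohort", but gives no intervals there. It then says: "All other analyses will be performed on the as-treated cohort". SAP 3.4 uses available data only, without imputation.

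**The concern.** A subject who meets 6.6 has, by definition, no device implanted, so the synopsis rule covers the same subject. Two sites could both comply with the protocol and stop following such a patient at very different times.

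This matters because the ITT safety rate is the only analysis in the SAP that includes subjects without an implant. Those subjects can still have primary events: Protocol 9.3 lists death, stroke, tamponade and myocardial infarction, four of the five components, among the risks of the procedure and anaesthesia. If they are in the ITT cohort but followed only to discharge, their 30-day status is not known by design.

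**Working it through.** The plan states no figure on this point that could be reproduced, and the table behind the sample size in Protocol 5.5.2 is blacked out. The check is mainly one of text, followed by an illustration of size.

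**Step 1: do the two follow-up rules cover the same patient?** Yes. The 6.6 patient was intended for treatment, was stopped at the procedure and has no implant. Study consent is scheduled at baseline, before implantation (Protocol Table 4), so this is a subject in the sense of the synopsis. The overlap is not total: a failed deployment may be a non-implanted subject without being a 6.6 screening failure. Within the overlap, the rules are discharge and 6 months.

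**Step 2: is that patient in the ITT cohort?** SAP 2.3 sets three conditions.

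| Condition | Status of a 6.6 patient |
|---|---|
| Consent | Met, if the Table 4 schedule is followed |
| Eligibility | Open. 6.6 speaks only of theoretical eligibility. A finding at the procedure may itself be an exclusion, such as item 21 of Protocol 6.2 ("Intra-cardiac masses, thrombi or vegetations"), whereas Protocol 7 has a central committee decide final enrolment. Neither document says whether a late finding removes the subject |
| Attempted | Open. Neither document says when an attempt starts, and 6.6 is not limited to stops before that point |

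**Step 3: does another rule recover day-30 status if 6.6 is followed?** None found.

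- SAP 3.4 (available data) accepts the gap.
- Protocol 6.5.2 recruits another patient, which does not supply the missing patient's status.
- Protocol 6.5.3 (lost to follow-up) deals with missed visits; under 6.6 none is due after discharge.
- Protocol 7.1 asks for unscheduled visits to be reported during the study period, which under 6.6 has ended for this patient.
- Protocol 10.3 follows adverse events to resolution; it does not detect new ones.

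**Step 4: size, as an illustration.** The number of events and of unobserved subjects are assumptions.

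Uncertainty per unobserved ITT subject = 1/n:

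- n = 60 (the planned maximum): 1/60 = 1.67 points
- n = 61 (if the 6.5.2 replacement rule is taken to apply): 1/61 = 1.64 points
- n = 30 (last column of the stopping table in Protocol 5.4, taken as a small-study case): 1/30 = 3.33 points

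With 3 subjects having events and 1 of 60 unobserved after discharge:

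- True rate: 3/60 = 5.00% or 4/60 = 6.67%
- Available-data rate, subject dropped from the denominator: 3/59 = 5.08%
- Error: 5.08 − 5.00 = +0.08 points, or 5.08 − 6.67 = −1.58 points (unrounded rates)
- If the subject is instead kept as a non-event: 3/60 = 5.00%, error 0 or −1.67 points

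Exact (Clopper-Pearson) 95% intervals: 3/60, 1.04% to 13.92% (width 12.88 points); 3/59, 1.06% to 14.15%; 4/60, 1.85% to 16.20%. Relative to the first width, 1.67/12.88 = 0.13.

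With more unobserved subjects and still 3 observed events:

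| Unobserved of 60 | Available-data rate | Possible true rate |
|---|---|---|
| 1 | 3/59 = 5.1% | 5.0% to 6.7% |
| 3 | 3/57 = 5.3% | 5.0% to 10.0% |
| 6 | 3/54 = 5.6% | 5.0% to 15.0% |

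The precision lost is small. What grows is the range of rates the data cannot distinguish.

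**The case against.** The best defence is that 6.6 is a specific rule for a named class and the synopsis line a general one. On that reading, 6.6 covers procedures abandoned before an attempt and the 6 months apply to attempted implants that failed. Then 6.6 patients are outside the ITT cohort and the day-30 gap does not arise. The exclusion criteria support this in part: a patient found to have a thrombus at the procedure arguably no longer meets eligibility on the plain wording of SAP 2.3. The reference there to required intervals may also point back to the synopsis, which would cover day 30.

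This is a plausible intention, but it is written nowhere. The synopsis has no exception, 6.6 is not confined to stops before an attempt, and its description of the patient as intended for treatment pulls the other way. Reading SAP 2.3 back to the protocol leads to the two conflicting intervals.

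Three parts of the objection stand. The ITT consequence is not established by the documents, only left possible. The effect per patient is small in a study with no pre-specified hypotheses (SAP 3.1). And the 3/59 figure assumes the subject leaves the denominator, which the SAP does not say outright; the alternative is shown above.

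**Conclusion.** The concern holds. The contradiction between Protocol 6.6 and the synopsis is certain on the text. Harm to the primary safety estimate requires four things together: 6.6 is followed rather than the synopsis, the subject is in the ITT cohort, discharge comes before day 30, and an event occurs between discharge and day 30 without being reported. The documents give no frequency for any of these. Events up to discharge are captured under either rule, and the as-treated analysis is unaffected.

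On the assumed counts, each unobserved subject leaves 1.7 points unresolved at n = 60 and 3.3 at n = 30. The direction of bias cannot be stated in advance. Because the study is descriptive and its size was chosen by the width of an exact interval (Protocol 5.5.2, SAP 1.5), what is at stake is the safety estimate and who is counted in it, not a test decision. This should be fixed, but it does not undermine the study.

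**What to change.** - Reconcile the synopsis, Protocol 6.6 and SAP 2.3 so that follow-up of subjects without an implant is stated once and identically.
- Define, in the same words in Protocol 6.6 and SAP 2.3, when an attempt starts. State whether 6.6 patients are in the ITT cohort; judging eligibility on information available before the attempt would settle this.
- Write the required follow-up interval for each cohort into SAP 2.3, so that every ITT subject has primary safety status ascertained through day 30, the endpoint's own horizon.
- Report the number of ITT subjects without day-30 status. Optionally, also give the ITT rate with none and with all of them counted as events.

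The cost is a few sentences in each document and at most a day-30 safety contact for a few subjects whom the synopsis already requires to be followed for longer.
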